7.5.1.1. Continuous Efficacy Endpoints

By-visit summary statistics for the following continuous measurements, including actual measurement, change from baseline, and percentage change from baseline, will be presented for the following:

- F-VASI/T-VASI
- F-BSA/T-BSA
- DLQI (or CDLQI) total score and subscores

Summary statistics, including sample size, mean, median, standard deviation, minimum, maximum, first quartile, third quartile, and 95% CI, will be presented by visits for both Cohorts A and B.

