APPENDIX E. PROTOCOL AMENDMENT SUMMARY OF CHANGES

Document	Date	
Amendment 1:	28 SEP 2020	
Amendment 2:	10 NOV 2020	

Amendment 2 (10 NOV 2020)

Overall Rationale for the Amendment:

The main purpose of this amendment is to add language to the Protocol to inform sites of alternative strategies to guarantee continuity of the clinical trial conduct and oversight in response to the COVID-19 pandemic.

1. Appendix D, COVID-19 Pandemic Mitigation Strategies and Instructions

Description of change: Added Appendix D to the Protocol and added cross-references to the appendix to relevant sections.

Rationale for change: To provide sites with Protocol-related guidance in response to the COVID-19 pandemic.

2. **Incorporation of administrative changes.** Other minor, administrative changes and clarifications have been incorporated throughout the Protocol and are noted in the redline version of the amendment.

Amendment 1 (28 SEP 2020)

Overall Rationale for the Amendment: The primary purpose of this amendment is to accommodate the EMA PDCO recommendation regarding the DLQI/CDLQI endpoint and to align the PK endpoints with those of parent studies INCB 18424-306 and INCB 18424 307.

1. Title Page; Section 1, Protocol Summary

Description of change: Added TRuE-V LTE to the Protocol title.

Rationale for change: To include the short name in the title.

2. Section 1, Protocol Summary (Table 1: Primary and secondary Objectives and Endpoints); Section 3, Objectives and Endpoints (Table 8: Objectives and Endpoints)

Description of change: Moved endpoint for DLQI/CDLQI from exploratory to secondary.

Rationale for changes: To address EMA PDCO recommendation.

2. Section 1, Protocol Summary (Table 1: Primary and Secondary Objectives and Endpoints); Section 3, Objectives and Endpoints (Table 8: Objectives and Endpoints)

Description of change: Moved endpoint for PK from exploratory to secondary.

Rationale for change: To align with INCB 18424-306 and INCB 18424-307 parent studies.

3. Section 1, Protocol Summary (Table 3: Schedule of Activities); Section 8.4, Pharmacokinetic Assessments

Description of change: Added clarifications that PK samples should be collected at predose and the time of the last study drug application is to be recorded in the eCRF.

Rationale for change: To align PK sample collection procedures with INCB 18424-306 and INCB 18424-307 parent studies.

4. Section 5.1, Inclusion Criteria (Inclusion Criteria 5a and 6)

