2.2. Study Objectives and Endpoints

Table 1 presents the endpoints and objectives.

Table 1: Objectives and Endpoints

| Objectives | Endpoints |
|---|--|
| Primary | • |
| To evaluate the duration of clinical response of ruxolitinib cream in participants with vitiligo. | For participants who are randomized in Cohort A: • Time to relapse (defined as < F-VASI75). |
| Key Secondary | |
| To evaluate the duration of clinical response of ruxolitinib cream in participants with vitiligo. | For participants who are randomized in Cohort A: • Time to maintain ≥ F-VASI90 response. |
| Secondary | |
| To further evaluate the efficacy of ruxolitinib cream. | Proportion of participants who achieve F-VASI50/75/90 during the extension treatment period. Actual measurements, change, and percentage change from baseline in F-VASI. Proportion of participants who achieve T-VASI50/75/90 during the extension treatment period. Actual measurements, change, and percentage change from baseline in T-VASI. Actual measurements, change, and percentage change from baseline in F-BSA. Actual measurements, change, and percentage change from baseline in T-BSA. Proportion of participants achieving a VNS of "4 – A lot less noticeable" or "5 – No longer noticeable" during the extension treatment period. |
| To determine the participants' quality of life. | Change from Week 52 in DLQI (or CDLQI) during the extension treatment period. |
| To evaluate the safety and tolerability of ruxolitinib cream. | The frequency and severity of AEs; includes performing physical examinations and collecting vital signs and laboratory data for hematology and serum chemistry. |
| To evaluate the ruxolitinib PK in plasma after treatment with ruxolitinib cream. | Trough plasma concentrations of ruxolitinib at Week 80 and Week 104. |

Table 1: Objectives and Endpoints (Continued)

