4.1.3. Baseline Value

For randomized participants not treated with any study drug, baseline is defined as the last nonmissing assessment before or on the day of randomization for all parameters.

For participants who continue in the extension treatment period, baseline is defined as follows:

- For efficacy evaluation, baseline is the last nonmissing measurement obtained before the first application of study drug in the parent study.
- For Cohort B safety evaluation, baseline is the last nonmissing measurement obtained before or on the day of first application of ruxolitinib cream in the parent study.
- For Cohort A safety evaluation,
 - For participants who are initially randomized to receive ruxolitinib cream in the
 extension treatment period (ie, Study INCB 18424-308), baseline is the last
 nonmissing measurement obtained before the first application of ruxolitinib cream
 in the parent study.
 - For participants who are initially randomized to receive vehicle cream in the
 extension treatment period (ie, Study INCB 18424-308), baseline is the last
 nonmissing measurement obtained before the first application of vehicle cream in
 the extension period.

When scheduled assessments and unscheduled assessments occur on the same day and time of the assessment or time of first application is not available, use the following convention to determine baseline:

- If both a scheduled and an unscheduled visit are available on the day of the first application and the time is missing, use the scheduled assessment as baseline.
- If all scheduled assessments are missing on the day of the first application and an unscheduled assessment is available, use the unscheduled assessment as baseline.

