7.2.5.5. Dermatology Life Quality Index

The DLQI is a simple, 10-question validated questionnaire to measure how much the skin problem has affected the participant over the previous 7 days (Finlay and Khan 1994). Participants aged \geq 16 years will answer the questionnaire with (1) very much, (2) a lot, (3) a little, or (4) not at all.

The questionnaire is analyzed under 6 headings as follows:

- Symptoms and feelings (Questions 1 and 2)
- Daily activities (Questions 3 and 4)
- Leisure (Questions 5 and 6)
- Work and school (Question 7)

- Personal relations (Questions 8 and 9)
- Treatment (Question 10)

The scoring of each question is as follows: Very much = 3; A lot = 2; A little = 1; Not at all = 0; Not relevant = 0; Question 7, "Prevented work or studying" = 3.

The following imputations will be applied for incorrectly completed questionnaires:

- If 1 question is left unanswered, this is scored 0 and the scores are summed and expressed as usual out of a maximum of 30.
- If 2 or more questions are left unanswered, the questionnaire is not scored.
- If Question 7 is answered "yes," this is scored 3. If Question 7 is answered "no," but then either "a lot" or "a little" is ticked, this is then scored 2 or 1. If "Not relevant" is ticked, the score for Question 7 is 0. If it is answered "no," but the second half is left incomplete, the score will remain 0.
- If 2 or more response options are ticked, the response option with the highest score should be recorded.
- If there is a response between 2 tick boxes, the lower of the 2 score options should be recorded.
- For the 6 DLQI subscales, if the answer to 1 question in a subscale is missing, that subscale should not be scored.

The DLQI is calculated by summing the score of each question, resulting in a maximum of 30 and a minimum of 0. The higher the score, the more quality of life is impaired.

The meaning of total DLQI scores can be categorized as follows:

- 0 to 1 =No effect
- 2 to 5 = Small effect
- 6 to 10 = Moderate effect
- 11 to 20 = Very large effect
- 21 to 30 = Extremely large effect

A change from baseline in DLQI and CDLQI score of at least 4 points is considered clinically important (Basra et al 2015, Waters et al 2010).

The questionnaire is also analyzed under 6 subscales as follows:

- Symptoms and feelings (Questions 1 and 2)
- Daily activities (Questions 3 and 4)
- Leisure (Questions 5 and 6)
- Work and school (Question 7)
- Personal relations (Questions 8 and 9)

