7.5. Analysis of Other Secondary Efficacy Parameters

7.5.1. Other Secondary Efficacy Analysis

All other secondary efficacy analyses will be conducted based on the FAS for Cohorts A and B separately. For Cohort A, only assessments on or before the first dose date of open-label rescue treatment will be summarized and all assessments will be listed.

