10.1. Changes to Protocol-Defined Analyses

The data from participants at Site 710 were removed from all efficacy analyses performed on the ITT-Ext population and FAS for the final CSR owing to noncompliance with the Protocol in the parent study resulting in serious concerns with the data quality. Data from participants at Site 710 were included in all other analyses because all participants at Site 710 applied study drug at least once.

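### The secondary DLQI/CDLQI endpoint is change from Week 52, but the SAP's analysis text computes change from the pre-treatment parent-study baseline, and this is not declared

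*SAP*

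**What the plan says.** Protocol Tables 1 and 4 and SAP Table 1 (SAP 2.2) give the quality-of-life endpoint in the same words: "Change from Week 52 in DLQI (or CDLQI) during the extension treatment period". In those tables the F-VASI, T-VASI, F-BSA and T-BSA change endpoints are stated from baseline, so DLQI/CDLQI was given its own reference point.

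SAP 7.5.1.1 handles all five alike. By-visit summaries, "including actual measurement, change from baseline, and percentage change from baseline, will be presented for the following", cover F-VASI/T-VASI, F-BSA/T-BSA and the DLQI (or CDLQI) total score and subscores. SAP 7.1 applies the same from-baseline rule to every continuous efficacy variable. SAP 4.1.3 fixes the reference: "For efficacy evaluation, baseline is the last nonmissing measurement obtained before the first application of study drug in the parent study".

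The only departure from the protocol that SAP 10.1 declares concerns one site: "The data from participants at Site 710 were removed from all efficacy analyses performed on the ITT-Ext population and FAS for the final CSR".

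**The concern.** A statistician who follows SAP 7.5.1.1 and 4.1.3 will compute change since before any treatment. The endpoint asks how quality of life moved during the extension, after participants had already used ruxolitinib cream for 28 to 52 weeks. The planned quantity adds the earlier change to the extension-period change. A group whose quality of life worsened during the extension could be shown as improved, in a study meant to assess durability after withdrawal and maintenance with continued use.

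The endpoint also has some standing. Protocol Appendix E records under Amendment 1: "Moved endpoint for DLQI/CDLQI from exploratory to secondary", in response to an EMA PDCO recommendation. As the visible SAP stands, this secondary endpoint has no matching analysis.

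**Working it through.** **Step 1. Is there a Week 52 reference anywhere in the visible SAP?**

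- SAP 4.1.3 has a randomization-day baseline, but only for randomized participants who never applied study drug. They are outside the FAS (SAP 5.3.1), and SAP 7.5.1 bases this analysis on the FAS.
- For treated participants, SAP 4.1.3 uses an extension-period reference once: for safety in the Cohort A vehicle arm, the last "nonmissing measurement obtained before the first application of vehicle cream in" the extension. It does not cover efficacy, the Cohort A ruxolitinib arm or Cohort B.
- SAP 4.1.1 defines Day 1 as the first application in the extension, but the efficacy baseline is defined separately from Day 1.
- The table list in SAP Appendix A names only a summary of DLQI and a summary of CDLQI. The shells are in a separate document.

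No visible text supplies the Week 52 reference.

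**Step 2. How do the two quantities differ?** For each participant:

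(visit − parent baseline) = (visit − Week 52) + (Week 52 − parent baseline), that is, SAP quantity = e + d,

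where e is the endpoint and d is the parent-study change. Higher scores mean worse quality of life, so e > 0 is worsening in the extension. The documents give no values for d or e. The range d = 0 to −4 is assumed. Its outer limit is the SAP's own threshold: "A change from baseline in DLQI and CDLQI score of at least 4 points is considered clinically important". That is a scale marker and not an estimate of the mean change. Values of e + d:

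| e | d = 0 | −0.5 | −1 | −2 | −3 | −4 |
|---|---|---|---|---|---|---|
| +0.5 | +0.5 | 0 | −0.5 | −1.5 | −2.5 | −3.5 |
| +1 | +1 | +0.5 | 0 | −1 | −2 | −3 |
| +2 | +2 | +1.5 | +1 | 0 | −1 | −2 |

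The signs are opposite only when 0 < e < −d. With d near 0 the two agree.

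**Step 3. Between arms in Cohort A.** With d = −2 in both arms, and e = +1 in one arm and 0 in the other, the difference from Week 52 is 0 − 1 = −1. From parent baseline it is (0 − 2) − (1 − 2) = −1. Randomization at Week 52 gives d the same expectation in both arms, so only chance imbalance and precision change. With equal SDs at the three times and equal correlations, the two changes have the same SD. If correlation decays with time (ρ between adjacent times, ρ² across both intervals), the ratio of SDs is √[(1 − ρ²)/(1 − ρ)] = √(1 + ρ). This is 1.14 at ρ = 0.3 and 1.34 at ρ = 0.8, with the parent-baseline change the more variable.

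**Step 4. Can the by-visit actual values stand in?** They can give the mean change only if Week 52 is displayed and the same participants contribute at both visits. The SD and CI of the change also need the within-participant correlation. In Cohort A, SAP 7.5.1 states that "only assessments on or before the first dose date of open-label rescue treatment will be summarized", so later means come from fewer participants. Let f be the share dropped after rescue, g the Week 52 mean score of those dropped minus that of those remaining, and e the mean change in those remaining. Then

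visit mean − Week 52 mean = e − f × g.

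For assumed f = 10% to 50% and g = 0.5 to 2 points, f × g runs from 0.1 × 0.5 = 0.05 to 0.5 × 2 = 1.0 point. The documents do not give the sign of g. If g = 0 the error vanishes; if g = −2 and f = 50% it is 0.5 × (−2) = −1.0.

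**The case against.** SAP Table 1 keeps the Week 52 wording, and SAP 7.5.1.1 is one shared sentence whose baseline is right for the VASI and BSA measures. The likeliest explanation is a drafting omission, not an intended switch. The shells are not visible, so a Week 52 change column may exist. The endpoint is descriptive: Protocol 10.3 plans no test of it, and SAP 3.2 calls all analyses exploratory. Actual values are summarized by visit and listed, and Cohort B has no rescue exclusion, so its mean change from Week 52 could be approximated from by-visit means if Week 52 is shown. All the magnitudes are assumed. The amendment log does not link the PDCO recommendation to the reference timepoint. Post-rescue data are left out whichever reference is used.

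Much of this stands as a limit. Nothing shows intent, no decision rule is affected, and the regulatory history shows the endpoint's standing but does not settle the reference. A Week 52 reference removes the Step 4 mismatch, but not the selection caused by leaving out post-rescue data. What does not stand is that nothing needs changing. Whatever the cause, the written rule gives a different quantity from the endpoint, the within-participant change with its SD and CI is not planned in any visible text, and a column in a shell would leave SAP Table 1 and SAP 7.5.1.1 in conflict.

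**Conclusion.** The concern holds and should be fixed. The SAP conflicts with the protocol and with its own Table 1, and the conflict is undeclared. The mismatch is established from the text; what the shells contain is not known.

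The discrepancy equals d, the mean parent-study change, which the documents do not give. Under the assumed range of 0 to −4 points, a worsening of 2 points since Week 52 would be reported as +2 to −2. A false impression of improvement requires that the parent-study gain exceed the extension-period worsening. The consequence is confined to within-group descriptive results. The expected Cohort A treatment contrast and the primary and key secondary analyses are unaffected.

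**What to change.** In SAP 4.1.3 and 7.5.1.1, define the DLQI/CDLQI reference as the Week 52 value: the last nonmissing score on or before first application in the extension. Report change from Week 52 by visit, cohort and treatment group with SD and 95% CI, and make the table shells match. Change from parent-study baseline may stay as a labelled supplementary summary. If the parent baseline is what is wanted, declare and justify it in SAP 10.1 and reconcile SAP Table 1. Dropping percentage change for these scores is optional.

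The cost is SAP wording and one derived variable. Protocol Table 3 already schedules the questionnaire at Week 52 and at the later visits, so no data collection changes.

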- Treatment (Question 10)

The CDLQI is the youth/children's version of the DLQI. For participants who are aged < 16 years at baseline (Day 1) of the parent study (INCB 18424-306 or INCB 18424-307), the CDLQI will be completed instead of the DLQI throughout their participation in this extension study.

The scoring of each question is as follows: Very much = 3; Quite a lot = 2; Only a little = 1; Not at all = 0; Question unanswered = 0; Question 7: "Prevented school" = 3.

The CDLQI is calculated by summing the score of each question, resulting in a maximum of 30 and a minimum of 0. The higher the score, the more quality of life is impaired.

The questionnaire is also analyzed under 6 subscales as follows:

- Symptoms and feelings (Questions 1 and 2)
- Leisure (Questions 4, 5, and 6)
- School or holidays (Question 7)
- Personal relationships (Questions 3 and 8)
- Sleep (Question 9)
- Treatment (Question 10)

The severity banding for CDLQI scores is as follows:

- 0 to 1 = No effect on child's life
- 2 to 6 = Small effect
- 7 to 12 = Moderate effect
- 13 to 18 = Very large effect
- 19 to 30 = Extremely large effect

The following imputations will be applied for incorrectly completed questionnaires:

- If 1 question is left unanswered, this is scored 0, and the scores are summed and expressed as usual out of a maximum of 30.
- If 2 or more questions are left unanswered, the questionnaire is not scored.
- If both parts of Question 7 are completed, the higher of the 2 scores should be counted.

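### SAP 7.5.1.1 plans percentage change from baseline for DLQI/CDLQI total and subscores, which is undefined at a baseline of 0 and unstable just above it, so the mean can point the opposite way to the absolute change

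*SAP*

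**What the plan says.** SAP 7.5.1.1 asks for by-visit summaries, "including actual measurement, change from baseline, and percentage change from baseline, will be presented for the following": F-VASI/T-VASI, F-BSA/T-BSA, and "DLQI (or CDLQI) total score and subscores". The statistics are given as "Summary statistics, including sample size, mean, median, standard deviation, minimum, maximum, first quartile, third quartile, and 95% CI", for each cohort.

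SAP 7.2.5.5 defines the scales. "The DLQI is calculated by summing the score of each question, resulting in a maximum of 30 and a minimum of 0", and likewise "The CDLQI is calculated by summing the score of each question, resulting in a maximum of 30 and a minimum of 0". On direction: "The higher the score, the more quality of life is impaired". Totals of 0 to 1 are labelled as no effect. In the DLQI, the lowest response and the not-relevant option both score 0. Several subscores rest on one item scored 0 to 3: DLQI Questions 7 and 10, and CDLQI Questions 7, 9 and 10.

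SAP 4.1.3 sets the efficacy baseline as the last value before the first study drug application in the parent study. SAP 7.1 plans percentage change where it is available, and SAP 4.1.4 imputes nothing for endpoints other than the primary and key secondary.

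The endpoint in SAP 2.2, and in Protocol Section 3, is "Change from Week 52 in DLQI (or CDLQI) during the extension treatment period". Both documents name percentage change for VASI and BSA endpoints, but not for DLQI or CDLQI.

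**The concern.** Percentage change needs a denominator that stays clear of 0. The other measures in the list meet this condition: parent-study inclusion criterion 2 (Protocol Appendix A) requires F-VASI of at least 0.5, T-VASI of at least 3, facial BSA of at least 0.5% and nonfacial BSA of at least 3%. No parent-study criterion sets a minimum DLQI or CDLQI.

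Two problems follow. A participant with a baseline of 0 has no percentage change and is left out of that row. The omission is selective, because such a participant can only stay at 0 or worsen. A participant with a baseline of 1 or 2 can contribute a very large positive percentage but never less than -100%, so a few low baselines can control the mean. The two effects pull in opposite directions, and the net bias cannot be known in advance.

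At stake is the reading of the quality-of-life tables (SAP Appendix A, Tables 2.9.2 and 2.9.3). Amendment 1 moved this endpoint from exploratory to secondary on a regulator's recommendation. A row that can contradict the absolute change in the same table invites a wrong reading.

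**Working it through.** The documents give no DLQI or CDLQI figure to reproduce. The check uses the scoring rules and hypothetical scores within the documented ranges.

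**Inputs**
- Range of totals: 0 to 30, higher is worse (SAP 7.2.5.5).
- Range of subscores: 0 to 3 for one item, 0 to 6 for two items (SAP 7.2.5.5).
- Denominator: value before parent-study treatment (SAP 4.1.3).
- Zero-baseline rule: none stated; no imputation (SAP 7.1 and 4.1.4).

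**Formulas**
- Absolute change = visit - baseline.
- Percentage change = 100 × (visit - baseline) / baseline, undefined when baseline = 0.

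**Step 1: asymmetry at a baseline of 1.** The best result is always 100 × (0 - 1)/1 = -100%. The worst is:
- one item: 100 × (3 - 1)/1 = +200%
- two items: 100 × (6 - 1)/1 = +500%
- total: 100 × (30 - 1)/1 = +2900%

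**Step 2: low nonzero baselines, no zeros.** Totals 1 to 3, 2 to 4, 20 to 10, 12 to 6.
- Mean change = (2 + 2 - 10 - 6)/4 = -3.0 points (better).
- Mean percentage change = (200 + 100 - 50 - 50)/4 = +50% (worse).
- The medians also disagree here: change (-6 + 2)/2 = -2 points, percentage (-50 + 100)/2 = +25%.

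One low baseline is enough. Totals 1 to 4, 10 to 5, 12 to 6, 20 to 10 give a mean change of (3 - 5 - 6 - 10)/4 = -4.5 points, against (300 - 50 - 50 - 50)/4 = +37.5%. In this set the median percentage stays at -50%.

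**Step 3: omission of zero baselines.** Totals 0 to 4, 0 to 3, 0 to 3, 4 to 2, 6 to 3.
- Mean change in all five = (4 + 3 + 3 - 2 - 3)/5 = +1.0 point (worse).
- Percentage change exists for two: (-50 - 50)/2 = -50% (better).

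**Step 4: a one-item subscore.** Six of ten participants at 0 and unchanged; the others go 1 to 3 and three times 3 to 2.
- Mean change in all ten = (2 - 1 - 1 - 1)/10 = -0.1.
- Mean percentage change in the four with a value = (200 - 3 × 33.3)/4 = +25%.

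**Step 5: how often, under assumptions.** A simulation drew total scores from gamma-Poisson distributions (60 participants, true 20% reduction, mean totals 2 to 10, gamma shape 0.7 to 1.5, 4000 data sets per setting). Between about 5% and 39% of participants had a baseline of 0. The mean change and the mean percentage change differed in sign in about 10% to 26% of data sets. These rates come from the assumed distributions, not from the trial documents.

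**The case against.** The strongest case against the point is that little depends on this row. Protocol 10.3 plans no formal tests beyond the primary and key secondary endpoints, and SAP 3.2 calls all analyses exploratory. Percentage change in DLQI is not a listed endpoint. The participant omitted from the percentage row still counts under actual value and absolute change. Sample size, median and quartiles are also planned, so a reader can see the smaller n and often the skew. All of this stands and limits the weight of the point. It does not repair the row: wording that allows unavailable values to be skipped is not a zero-baseline rule, and a lower n does not show that those left out could not have improved.

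A reader might also infer something stronger: that Cohort A responders, being nearly clear of facial vitiligo at Week 52, would score 0 there, so that worsening after withdrawal could never appear. The documents do not support this. The denominator is the score before parent-study treatment, not the Week 52 score, and response at Week 52 gives no reason to expect a pre-treatment score of 0. Someone at 8 before treatment, 0 at Week 52 and 6 after withdrawal has 100 × (0 - 8)/8 = -100% and then 100 × (6 - 8)/8 = -25%, so the loss of benefit is visible. No percentage change from Week 52 is planned.

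The examples were built to show that the signs can differ. In the simulation, reversal was the less common outcome.

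**Conclusion.** The point holds in a narrow form. SAP 7.5.1.1 orders, as written, a mean percentage change with a 95% CI on scales that can be 0 at baseline. It has no rule for that case, and the result can disagree in sign with the mean absolute change. This follows from the scoring rules alone.

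The size in this trial is unknown, because the documents give no distribution of DLQI or CDLQI scores. It depends on how many participants had a score of 0, 1 or 2 before parent-study treatment. One-item subscores, with only four possible values, are the most exposed.

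The consequence is limited to one untested descriptive row. It does not affect the primary or key secondary analysis, and it does not remove anyone from the DLQI analysis as a whole. It is still worth correcting, because the row can mislead and nothing in the stated endpoints needs it.

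**What to change.** In SAP 7.5.1.1, limit percentage change to F-VASI/T-VASI and F-BSA/T-BSA. For DLQI and CDLQI total and subscores, report the actual score and the absolute change.

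In the same edit, state that absolute change is also summarised from Week 52. SAP 2.2 and Protocol Section 3 define the endpoint from Week 52, but SAP 7.5.1.1 read with SAP 4.1.3 gives only change from the parent-study baseline. Deleting the percentage row alone would leave the stated endpoint without a planned summary in that section.

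If the sponsor prefers to keep the percentage row, the minimum is a stated zero-baseline rule and the number of participants excluded at each visit.

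A summary of the share changing by at least 4 points in total score, the threshold cited in SAP 7.2.5.5, is optional and would be a new output.

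The cost is a few words in the SAP and matching edits to the table shells. No new data are needed and no endpoint changes. One set of statistics is removed and the Week 52 change is added.
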